## 1.6 Statistical Analysis Plan

**1.6.1 Analytic plan.** Statistical analysis will follow good practices for the evaluation of randomized controlled trials as embodied in the CONSORT statement. Missing data will be imputed using a multiple imputation approach and outcome models averaged across imputations to adhere to the intent-to-treat principle. We will compare the sensitivity of the findings to alternative methods for handling missing data (see Missing Data Section below).

As a preliminary step, demographics, baseline weight and health history will be summarized across the aggregate sample and compared between cells (intervention components) using Analysis of Variance (ANOVA) for continuous variables, chi-squared analyses for categorical variables and non-parametric tests as appropriate. Variables will be considered potential confounders in the subsequent models if these variables are correlated with the outcome under consideration (at a modest  $p < .30$  level). The distribution of each of study outcome will be assessed using both parametric and graphical methods and transformed as necessary (e.g. log transform towards normality). Potential distributions for the outcome variables

include normal and binomial, and zero-inflated distributions.

Evaluation of the intervention components will involve generalized linear models that regress percent weight change from baseline (e.g., normal distribution & identity link function) and achievement of a  $\geq 5\%$  weight loss (binomial distribution & logit link function) on effect-coded indicators for each of the five intervention components and unique 2 through 5-way interactions of components. Effect coding  $(-1,1)$  is essential in analyzing factorial designs and results in regression weights that correspond to main effects and interactions.

Effect-coded main effects and interactions are orthogonal to one another, yielding unbiased estimation of standard errors, and equal power for main effects and interactions for given effect sizes. Using this approach, individual cell sizes (for each combination of components) does not limit statistical power. Models will adjust for confounders identified during preliminary analyses, including demographics, health and weight history that are associated with weight loss outcomes.

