**1.6.2 Missing data.** Analyses will be conducted on the intent-to-treat sample (everyone randomized will be included in the final analysis) under various assumptions about the missing data mechanism. Sensitivity to these assumptions will be tested. Specifically, we will gather follow-up information and reasons for dropout regardless of protocol completion and censor at the point of loss. We will compare the robustness of our findings using three statistical approaches for handling missing data. First, we will use a multiple imputation approach to impute missing outcomes. Next, we will use inverse probability weighting with propensity scores. This is a two-step method: 1) using logistic regression, the probability of missingness is modeled as a function of baseline covariates and baseline values of the outcome and 2) the inverse of the propensity scores (predicted probabilities of dropout from the first step) serve as weights in our regression model of the outcomes. Provided the data are missing at random (MAR) or that the probability of missingness can be fully explained by observable data, this approach produces asymptotically unbiased estimates. To allow for the possibility that the MAR assumption may not hold, we will also use a third approach, pattern mixture models, in which the distribution of the outcome is assumed to follow a mixture of two distributions: one for those who complete follow up and another for those who do not.

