**1.6.3 Sample size and power estimates.** Following the full factorial design, each of the planned 384 participants is randomly assigned to each of the five intervention components. There are 32 possible combinations of intervention components, but each component will be administered to 192 persons and withheld from 192 persons. Using the generic approach described by Lehr, a sample size of  $n = 192$  per group permits the detection of standardized effect sizes (SEs) of  $\Delta = (4/n^{.5})$  (where 4 encompasses standard assumptions of a type-I and type-II error rate of  $\alpha = .05$  and  $\beta = 20\%$ , respectively where  $4 \approx \sqrt{2} \times (|z\alpha/2 + z\beta|)$ , and solves to  $SE = 0.29$ ). According to estimates based on our preliminary data, RxWL without additional intervention components produces  $\geq 5\%$  weight loss for 50% of the sample, and the standard deviation on percent weight change will be 5.8% at 12-months. This generic approach estimates power to detect intervention component effects of 9% on proportion achieving  $\geq 5\%$  weight loss and effects of 1.7% on mean weight loss. Statistical power was further evaluated using Monte Carlo estimation, the model specification (with effect coding) for the proposed study, and parameter estimates based on previous RxWL trials. This tailored approach yielded estimates of 91% power to detect a component marginal effect size of  $ES = 0.16$  or an additional 3% achieving  $\geq 5\%$  weight loss and just under 1% additional weight loss due to component effects. The study is adequately powered because a lesser effect would not be clinically significant.

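### The inverse-probability-weighting sensitivity analysis weights by 1/P(dropout) instead of 1/P(observed), so its claimed unbiasedness under missing at random does not hold in general

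*Combined protocol and SAP*

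**What the plan says.** Section 1.6.1 makes multiple imputation the main method: "Missing data will be imputed using a multiple imputation approach and outcome models averaged across imputations to adhere to the intent-to-treat principle". Section 1.6.2 then sets up the comparison: "We will compare the robustness of our findings using three statistical approaches for handling missing data". These are multiple imputation, inverse probability weighting and pattern mixture models.

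The weighting is described in two steps. In the first, "using logistic regression, the probability of missingness is modeled as a function of baseline covariates and baseline values of the outcome". In the second, "the inverse of the propensity scores (predicted probabilities of dropout from the first step) serve as weights in our regression model of the outcomes". The section adds that, if data are missing at random, "this approach produces asymptotically unbiased estimates".

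Both steps name the same quantity, the probability of being missing. The probability of being observed or retained appears nowhere in sections 1.6.1 to 1.6.3.

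**The concern.** Only participants with an observed outcome enter the weighted regression. The weights should make them stand in for everyone randomized, so completers who resemble the dropouts must count for more. Dividing by the probability of dropout does the opposite: it gives most weight to completers who were least likely to leave.

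Weighting is one of only three approaches compared. If it is coded as written, a disagreement with multiple imputation could come from the inverted weights alone, and agreement would not show that the result is robust under missing at random. Effect modification, which turns the inversion into bias in a component effect, is something the trial itself looks for: Aim 2 in section 1.1 plans moderator analyses.

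**Working it through.** The plan attaches no figure to this analysis, so there is none to reproduce. The check is algebra followed by illustrations.

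**1. Algebra.** Let p(X) be the probability of dropout given baseline covariates X, and f(X) the distribution of X among those randomized. Completers weighted by w(X) have a covariate distribution proportional to f(X)(1 − p)w.
- With w = 1/(1 − p) this is f(X), the randomized population.
- With w = 1/p it is f(X)(1 − p)/p, which differs from f(X) unless p is constant.

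**2. Individual weights.** At p = 0.05, 1/p = 20 and 1/(1 − p) = 1.05. At p = 0.40, 1/p = 2.5 and 1/(1 − p) = 1.67. The order is reversed.

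**3. Two equal strata.** Assume success rates of 60% and 40%, averaging the 50% in section 1.6.3, and component effects of 15 and 3 points, averaging the 9 points given there. Assume dropout of 10% in stratum A and 30% in stratum B.
- As written, the strata carry 0.9/0.1 = 9 and 0.7/0.3 = 2.33. A's share is 9/11.33 = 79%. Success is 0.794 × 60 + 0.206 × 40 = 55.9%. The effect is 0.794 × 15 + 0.206 × 3 = 12.5 points.
- Unweighted, A's share is 0.9/1.6 = 56%, giving 51.2% and 9.8 points.
- Correctly weighted, the strata carry 0.9/0.9 = 1 and 0.7/0.7 = 1, giving 50.0% and 9.0 points.

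The as-written effect is 10.9 points at 15%/25% dropout and 13.9 at 5%/35%. At 20%/20% it is 9.0, with no bias.

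**4. Mean weight loss.** From section 1.6.3: SD 5.8% and a component effect of 1.7 points. Assumed: mean loss 5% (from 50% reaching 5% under normality), a standard normal covariate correlated 0.4 with outcome (0.4 × 5.8 = 2.32 points per SD), 20% dropout, and dropout log-odds falling by s per SD. The component effect rises by m points per SD.

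With logistic dropout, (1 − p)/p is proportional to exp(sX). The as-written weights therefore shift the covariate mean from 0 to s. The crude mean becomes 5 + 2.32s and the component difference 1.7 + ms. The overall dropout rate cancels.

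| Slope s | 0.25 | 0.5 | 1.0 |
|---|---|---|---|
| Crude mean, as written (truth 5.0) | 5.6 | 6.2 | 7.3 |
| Crude mean, unweighted | 5.1 | 5.2 | 5.4 |
| Difference as written, m = 0 (truth 1.7) | 1.70 | 1.70 | 1.70 |
| m = 0.2 | 1.75 | 1.80 | 1.90 |
| m = 0.4 | 1.80 | 1.90 | 2.10 |
| m = 0.85 | 1.91 | 2.13 | 2.55 |
| Effective sample as written, % of completers | 96 | 84 | 44 |
| Effective sample, correct weights | over 99 | 99 | 95 |
| Power for 1.7 points, m = 0, as written | 78% | 72% | 53% |
| Power, correct weights | 80% | 79% | 78% |

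A simulation of 2,000,000 participants agrees with the differences to about 0.01, and correct weights return 1.68 to 1.69 throughout. Adjusting for the covariate brings the mean back to 5.0 but leaves the component bias: 1.90 at m = 0.2 and 2.55 at m = 0.85, both at s = 1.0. Power comes from 4,000 simulated trials per case at N = 384, with a fitted logistic first step, covariate-adjusted weighted regression and sandwich standard errors. The other four components and the interactions were not simulated.

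**The case against.** The plan names a standard method and states its standard property, so the parenthesis may be loose wording that any analyst would put right. Harm arises only if it is coded literally. Even then, bias in a component effect needs three things together: a covariate that drives dropout, modification of the component effect by that covariate, and no term for that interaction in the outcome model. The bias is also modest in the milder cases. At slopes of 0.25 and 0.5 with modification of 0.2 to 0.4 it is 0.04 to 0.20 points, against an empirical SD of about 0.61 to 0.70 for the estimate at N = 384. For the responder outcome, a crude large-sample check over the same cases gave 11.9 to 12.6 points against about 11.7. The large figures need a slope of 1.0. Multiple imputation and pattern mixture models are unaffected, and no rule selects or rejects a component on the weighted result.

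All of this stands as a limit on size. The crude means matter little too, since section 1.6.1 plans adjusted models. It does not rescue the text. The parenthesis defines the weight, and the unbiasedness claim fails in general for that weight. An analyst who follows the plan codes the wrong estimator, and one who corrects it silently departs from the plan. The bias has the sign of m × s, so it can also shrink a real effect.

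**Conclusion.** The concern holds. As written, the weight is 1/P(dropout), and the claim of asymptotic unbiasedness under missing at random is not true in general for it. The error is confined to one sensitivity analysis.

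Under logistic dropout on a normal covariate, the bias in the mean-loss component difference is m × s: 0.05 to 0.40 points on a true 1.7 for modification of 0.2 to 0.4 per SD and slopes of 0.25 to 1.0. It is zero when the component effect is homogeneous or dropout is constant. In the homogeneous case with uneven dropout, the cost is precision: at an assumed 20% dropout, power falls by 2, 7 and 25 percentage points at the three slopes. Whenever effect modification was present in these illustrations, the written weights did worse than no weighting.

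The size rests on assumed dropout, slopes and modification. The direction of the weighting error rests only on the text and the algebra.

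**What to change.** In section 1.6.2, replace the second step with wording such as: the inverse of the predicted probability of having the outcome observed, 1/(1 − predicted probability of dropout), serves as the weight for participants with observed outcomes. The unbiasedness statement should then be made conditional on a correctly specified missingness model. Stating that robust (sandwich) standard errors will be used is a sensible companion, though separate from correcting the weight.

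This corrects the weight only. The first step lists baseline covariates and the baseline outcome value, with no component term, so dropout that differs by component would not be addressed by this change.

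The cost is one sentence in the plan, with no added data and no burden on participants.

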**1.4.2 Participant recruitment and enrollment.** Participants will be recruited via advertisements in local media (e.g. newspapers, radio); targeted online advertising (e.g., Facebook, Google AdWords); flyers and advertisements posted in waiting rooms and exam rooms in primary care offices used in previous studies of RxWL; informational materials made available as part of the health and wellness program for employees in the Lifespan Heath System and hospital network (an approach used in a previous RxWL trial); and direct mailings. A screener completed online or by phone will be used to determine initial eligibility. Individuals who appear eligible will be invited to attend an orientation session at the research center. The study will be described in detail and participants will have the opportunity to complete informed consent, begin the baseline assessment, and schedule their randomization visit. Participants are required to complete the baseline assessment, including wearing the physical activity monitor and completing dietary recalls (described below), to be eligible for randomization.

**1.4.3 Randomization.** Prior to enrollment, a randomization schedule will be prepared based on 12 blocks of 32 patterns of assignment to each of the five intervention components. A sequentially-numbered sealed envelope containing the assignment will be opened by research staff at the time of randomization. The participant will receive brief written materials explaining their assignment and how to begin treatment via the online system. Further orientation to the treatment system is conducted online via interactive video lesson. Study staff will be available by phone to trouble-shoot technical difficulties, but no human-delivered weight loss counseling will be provided in-person or by phone. Participants will be enrolled until the total N=384 target enrollment has been satisfied.

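### The generic calculation of the detectable mean effect counts all 384 randomized participants as having a 12-month weight; no allowance for attrition is stated

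*Combined protocol and SAP*

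**What the plan says.** Enrolment (section 1.4.3) has a fixed end point: "Participants will be enrolled until the total N=384 target enrollment has been satisfied". The randomization schedule of 12 blocks of 32 patterns gives the same total.

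Section 1.6.3 takes half of that total as the group size for each component: "each component will be administered to 192 persons and withheld from 192 persons". It applies Lehr's formula with two-sided alpha 0.05 and beta 20% and reports 0.29 SD. It then assumes that "the standard deviation on percent weight change will be 5.8% at 12-months" and converts the effect to 1.7 points of mean weight loss.

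The same section gives a Monte Carlo figure of 91% power at an effect size of 0.16. The inputs are said to come from earlier RxWL trials but are not listed. The sentence declaring the study adequately powered follows directly after this figure.

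Section 1.6.2 foresees losses: "we will gather follow-up information and reasons for dropout". It plans multiple imputation, inverse probability weighting and pattern mixture models, and includes everyone randomized in the final analysis. No expected dropout rate, retention target or inflation of the sample size is given.

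**The concern.** Weight is measured at an assessment by a blinded assessor using a digital scale (sections 1.5 and 1.5.1), so a missed 12-month assessment is a missing primary outcome. The generic calculation has no term for this, although the analysis section is written on the footing that it will happen.

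Keeping everyone in the analysis does not close the gap. Multiple imputation retains 384 rows, but the between-imputation variance carries the missing information into the standard error. Inverse probability weighting uses only the observed outcomes. Neither method by itself gives back the precision of 192 measured weights per level.

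The experiment decides which components enter the optimized package. A reader faced with a null main effect needs to know what effect the trial could realistically have detected, and the 1.7-point figure is one of the numbers that reader would use.

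**Working it through.** **Inputs.** From the plan: N = 384, 192 per level, two-sided alpha 0.05, power 80%, SD 5.8 points (sections 1.4.3 and 1.6.3). Assumed, because the plan gives no rate: attrition *a* of 5 to 30%, equal across the levels of each component.

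**Step 1: reproduce the plan's figure.** Detectable effect = 4/√n = 4/√192 = 0.289 SD; 0.289 × 5.8 = 1.67 points. These are the stated 0.29 and 1.7. With the unrounded constant √2 × (1.960 + 0.842) = 3.962, the results are 0.286 SD and 1.66 points. The figures reproduce with all 192 per level counted, so no allowance is hidden in them.

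**Step 2: find the slack.** The number per level needed for 80% power is 2 × (1.960 + 0.842)² / d².
- For 1.7 points, d = 1.7/5.8 = 0.293 and n = 183. Tolerable loss is 1 − 183/192 = 4.7%.
- For 0.29 SD, n = 187. Tolerable loss is 1 − 187/192 = 2.6%.
- For the unrounded 0.289 SD, n = 189. Tolerable loss is 1 − 189/192 = 1.6%.

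The slack comes only from rounding the constant and the effect, and is about 5% on the most lenient reading.

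**Step 3: apply attrition.** n = 192(1 − a); detectable effect = 4/√n; power = Φ(d√(n/2) − 1.96).

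| Assumed loss | n per level | Detectable (SD) | Detectable (points) | Power for 0.289 SD | Power for 1.7 points |
|---|---|---|---|---|---|
| 0% | 192 | 0.289 | 1.67 | 80.7% | 81.9% |
| 5% | 182.4 | 0.296 | 1.72 | 78.7% | 79.9% |
| 10% | 172.8 | 0.304 | 1.76 | 76.5% | 77.8% |
| 20% | 153.6 | 0.323 | 1.87 | 71.6% | 72.9% |
| 30% | 134.4 | 0.345 | 2.00 | 65.8% | 67.1% |

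These are complete-case approximations without covariate adjustment.

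**Step 4: the ≥5% outcome.** Section 1.6.3 takes a reference rate of "weight loss for 50% of the sample" and reports a detectable effect of 9 points. A two-sided comparison of 50% with 59% at 192 per level has 42.5% power with no attrition at all. The difference detectable at 80% power is about 14 points, and 9 points would need 480 per level. Attrition is therefore not the main fault in that figure.

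**The case against.** Several points on the other side have force.

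- **The Monte Carlo result.** A reader might infer that all the power figures in section 1.6.3, including the 91%, assume complete data. The documents do not support that. They state neither the number with outcomes nor the missingness used in the simulation, and inputs from earlier trials may have included attrition. The adequacy sentence follows the Monte Carlo figure and most naturally refers to it, so the generic calculation cannot be said to be what that sentence rests on.
- **No dropout rate is given.** A reader might infer that the stated effects will not be achieved. That is not established. At 5% loss, power for 1.7 points is 79.9%, essentially the target. The plan also has features that favour retention: a full baseline assessment before randomization, payment for each follow-up assessment, and follow-up regardless of protocol completion.
- **Covariate adjustment.** Section 1.6.1 adjusts for variables associated with weight loss. For the mean outcome, the detectable effect scales with √((1 − R²)/(1 − a)), so an R² of 0.10 would offset 10% loss and 0.20 would offset 20%. No R² is given, so this gain is possible but cannot be counted on.
- **Imputation from interim weights.** A reader might treat the tabulated losses as upper bounds, on the ground that 3- and 6-month weights would recover part of the information. The plan does not say that the imputation model uses them, and variable inverse probability weights can cost precision beyond the loss in numbers. The table is an approximation, not a bound.

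What stands after this is narrower but clear: the generic calculation makes no allowance for losses that the plan itself foresees, and it has almost no slack.

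**Conclusion.** The point holds for the generic calculation of mean weight loss. The 0.29 SD and 1.7 points are correct arithmetic on an unstated assumption of complete 12-month data. Without help from covariate adjustment, 80% power for 1.7 points is lost once attrition passes about 5%.

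The decline is gradual. At 10% loss the detectable effect rises by about 0.09 points (1.67 to 1.76), and at 30% by about 0.33 points (1.67 to 2.00). These sizes rest on an assumed loss rate, equal loss across levels, the plan's SD of 5.8, and an unadjusted complete-case approximation.

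This is an omission to put right in the text. It is not evidence that the trial is too small, and it says nothing either way about the Monte Carlo result. The 9-point figure for the ≥5% outcome fails with complete data and is a separate matter.

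**What to change.** Keep N = 384 and change section 1.6.3 as follows.

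1. State the assumed 12-month retention. The section already draws on earlier RxWL trials, so their retention is the natural source. If it is not available, show a range such as 10 to 30% loss.
2. Restate the generic detectable mean effect for the number expected to have a 12-month weight. Any allowance for covariate adjustment should be given separately, with the R² assumed.
3. Say whether the Monte Carlo evaluation included missing outcomes. If it did, report the rate; if not, rerun it with the same missingness and the planned handling of missing data.
4. Correct the 9-point figure for the ≥5% outcome separately. Adjusting it for attrition would not repair it.

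The cost is SAP wording and possibly one rerun of the simulation, with no extra enrolment and no change to the analysis. The detectable mean effect becomes somewhat less favourable. Correcting the 9-point figure is a larger change, to about 14 points even with complete data.

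### The stated detectable effect of 9 points on the proportion with ≥5% weight loss is wrong: the plan's own formula and 50% base rate give about 14 points, and power at 9 points is about 42%

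*Combined protocol and SAP*

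**What the plan says.** Section 1.6.3 of the combined protocol and SAP plans 384 participants in a full factorial design, so that "each component will be administered to 192 persons and withheld from 192 persons". It uses Lehr's rule, with a detectable standardized effect of 4/√n, "where 4 encompasses standard assumptions of a type-I and type-II error rate of" 0.05 and 20%, and obtains 0.29. Its outcome assumptions for RxWL without added components are ≥5% "weight loss for 50% of the sample, and the standard deviation on percent weight change will be 5.8% at 12-months".

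From these inputs it states: "This generic approach estimates power to detect intervention component effects of 9% on proportion achieving" ≥5% weight loss, and 1.7% for mean weight loss. A separate Monte Carlo estimate follows: 91% power for a standardized effect of 0.16, described as an additional 3% reaching the threshold and just under 1% additional weight loss.

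Aim 1 (section 1.1.1) names the proportion reaching ≥5% first and mean weight loss second. Section 1.6.1 models both.

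**The concern.** One sentence applies one standardized effect to two outcomes. To return to the natural scale, that effect is multiplied by the outcome's standard deviation. For the mean this gives the stated 1.7. For a proportion the standard deviation is fixed by the base rate, and at 50% it takes its largest value, 0.5. The result should then be about 14 points, well above 9.

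The trial exists to decide which components go into an optimized package. If the plan says it can detect 9 points when its 80%-power difference is about 14, a non-significant result on this outcome will be read as evidence against a 9-point benefit. In fact the binary test would miss a true 9-point benefit more often than it found one.

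**Working it through.** **Inputs, all from section 1.6.3.** n = 192 per level; two-sided α = 0.05 (the constant uses z at α/2); power 80%; base rate 50%; SD of percent weight change 5.8.

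**Step 1. The standardized effect reproduces.** 4/√192 = 0.2887, stated as 0.29. With the unrounded constant, √2 × (1.960 + 0.842)/√192 = 0.286.

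**Step 2. The mean figure reproduces.** 0.2887 × 5.8 = 1.67, stated as 1.7. Power at 1.7 with 192 per level is 82%.

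**Step 3. The proportion figure does not.** SD = √(0.5 × 0.5) = 0.5, so 0.2887 × 0.5 = 0.144, or 14.4 points. Other routes from the same inputs:

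| Method | Detectable difference from 50% |
|---|---|
| Lehr | 14.4 points |
| Pooled two-proportion formula, 80% power | 14.1 points |
| Arcsine effect size of 0.289 | 14.2 points |
| Logit conversion of 0.289 | 12.8 points |
| One-sided test | 12.6 points |
| 384 per arm in place of 192 | 10.0 to 10.2 points |
| 0.29 read directly as a log odds ratio | 7.2 points |

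None gives 9. Working backwards, 0.09/0.2887 = 0.312, and √(p(1 − p)) = 0.312 needs p of about 11% or 89%. The plan states 50%.

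**Step 4. Power at the stated effect.** For 50% versus 59% with 192 per level, the pooled two-proportion formula gives 42.5%; an exact binomial calculation of the Pearson test gives 41.6%. Power of 80% at 9 points needs about 480 per level, or 2 × 480 = 960 in total, which is 2.5 times the planned 384.

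**Step 5. Higher base rates.** Participants without a given component receive on average two of the other four, so their rate could exceed 50%. The plan gives no such rate; these values are assumptions.

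| Assumed rate without the component | Detectable difference, 80% power | Power at 9 points |
|---|---|---|
| 50% (stated) | 14.1 points | 42% |
| 60% | 13.4 points | 45% |
| 70% | 12.2 points | 53% |
| 72% | 11.8 points | 55% |

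**Step 6. Loss to follow-up.** Section 1.6.3 makes no allowance. With none, power at 9 points is 42%. If 20% of the information were lost (an assumption, 154 per level), it would be 35%.

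**Step 7. The two stated effects are not equivalent.** If percent weight change is normal with SD 5.8 and half the sample reaches 5%, a shift of 0.2887 SD moves Φ(0.2887) − 0.5 = 11.4 points across the threshold. Binary power at 11.4 points is about 61%, against about 80% for the same shift on the continuous scale.

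**The case against.** The arithmetic itself is hard to dispute. The case against giving it weight has four parts.

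- **The binary test does not act alone.** Section 1.1 uses and/or between the two outcomes, section 1.5.1 defines the primary measure through weight and percent weight loss, and the a priori optimization criteria are not spelled out as significance on the proportion. Under the normal model of step 7, a 9-point gain from 50% is a shift of 0.23 SD, or 1.3% of weight. The continuous test has about 60% power for that shift, and at least one of the two tests succeeds about 64% of the time (simulation, no multiplicity correction). This stands: the statement that a 9-point effect is more likely missed than found applies to the binary test only, and exclusion of such a component is a risk rather than a certainty.
- **The adequacy conclusion follows the Monte Carlo estimate, not the 9%.** True, but that estimate is presented as a further evaluation and does not produce 9%. Nor does a simple calculation support it: with 192 per level, power is about 8% for 3 points from 50% and about 35% for a between-group standardized difference of 0.16. That statement needs its own reconciliation.
- **Covariate adjustment could help.** Treated as variance reduction, it would have to remove about 60% of the outcome variance (1 − 192/480 = 0.60). The plan claims nothing of that size, and the generic calculation contains no covariates.
- **It is one figure in a power section.** Correcting it changes no model, allocation or sample size. That makes the correction cheap. It does not make a wrong power claim for a named outcome acceptable.

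**Conclusion.** The concern holds. On the plan's own inputs (192 per level, two-sided 0.05, 80% power, 50% base rate) the detectable difference in the proportion with ≥5% weight loss is about 14 points. The stated 9 is a little over a third too small: (14.1 − 9)/14.1 = 36%. Power at 9 points is about 42%. These two results need no outside assumption. The higher base rates, the 20% information loss and the normal-model equivalence do rest on assumptions, and the error does not depend on any of them. The error is confined to the binary outcome; the 1.7% figure for mean weight loss is right.

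**What to change.** In section 1.6.3, replace the 9% with about 14 percentage points (50% versus 64%) at 80% power, and state that power at 9 points is about 42%. Say that percent weight change, rather than the ≥5% proportion, carries most of the trial's sensitivity, so that a null result on the proportion is not read as ruling out a 9-point effect.

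If the 9% came from another calculation, give its method and base rate instead. In the same edit, reconcile the corrected figure with the Monte Carlo statement; otherwise 14 points at 80% power will stand beside 3 points at 91%.

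The cost is wording in the SAP and a less favourable stated figure. No participants, procedures or models change.
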